- 1. Has received more than 24 hours (ie, a single dose of a daily therapy or the recommended daily frequency of a short acting therapy) of a potentially effective systemic antibacterial treatment within the 72 hours prior to the first dose of test article. A subject will be considered to have received a potentially effective systemic antibacterial treatment if the pathogen identified as causing infection is shown to be susceptible to the antibacterial given or, in the circumstance where a pathogen is not identified, if the antibacterial agent is approved for treatment of pneumonia or is known to have activity against any of the leading causes of CABP (eg, *Streptococcus pneumoniae, Haemophilus influenzae, Moraxella catarrhalis, S. aureus, Legionella pneumophila*).
- 2. Is known or suspected to have CABP caused by a pathogen that may be resistant to test article (eg, *Pseudomonas aeruginosa*, *Proteus* spp., *Morganella morganii*, *Providencia* spp., *Pneumocystis jiroveci*, obligate anaerobes, mycobacteria, fungal pathogens).
- 3. Suspected or confirmed empyema (a parapneumonic pleural effusion is not an exclusion criterion) or lung abscess.
- 4. Subjects who reside in a long-term care or subacute/intermediate healthcare facility (eg, nursing home) or a subject diagnosed with pneumonia following a recent hospitalization (overnight admission within 90 days prior to current admission).
- 5. Has a known history of having experienced unstable cardiac disease (eg, unstable angina, myocardial infarction, acute congestive heart failure, unstable cardiac arrhythmia) within the 3 months prior to Screening or presents with a tachyarrhythmia (excluding sinus tachycardia).
- 6. Has any of the following at Screening:
 - alanine aminotransferase (ALT) or aspartate aminotransferase (AST) ≥ 3 × Upper Limit of Normal (ULN)
 - total bilirubin $> 1.5 \times ULN$
 - suspected or confirmed clinical evidence of end-stage liver disease (eg, ascites, hepatic encephalopathy)
- Requires any form of dialysis (eg, hemodialysis, peritoneal dialysis), has a history or evidence of severe renal disease, or has a calculated creatinine clearance (CrCl) of < 30 mL/minute, using the Cockcroft-Gault equation (see calculation in Appendix 2).
- 8. Significant immunological compromise determined by any of the following:

- Current or anticipated neutropenia defined as < 500 neutrophils/mm³

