7.5 Test Article Administration

7.5.1 Oral Treatment

Subjects should receive their first dose of test article on the morning following enrollment.

All doses of oral test article should be taken with water.

All oral doses should be taken in a fasted state. Fasting is defined as no food, antacids, or multivitamins containing multivalent cations (eg, aluminum, magnesium, calcium, bismuth, iron, or zinc) or drink except water for at least 6 hours before dosing. After dosing, no food is permitted for 2 hours as well as no dairy products, antacids, or multivitamins containing multivalent cations (eg, aluminum, magnesium, calcium, bismuth, iron, or zinc) for 4 hours.

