10 DATA HANDLING CONVENTIONS

10.1 Premature Withdrawal and Missing Data

If available, pharmacokinetic parameters from the concentration-time profile data of patients who drop out or are withdrawn will be calculated but will be excluded from the final statistical analysis.

For all variables, only the observed data from the patients will be used in the statistical analyses, i.e., there is no plan to estimate missing data, unless otherwise specified.

Missing data occurs when any of the requested data is not provided, leading to blank fields on the collection of the instrument. These data will be indicated by the use of a "blank" in subject listing displays. Answers such as "Not applicable" and "Not evaluable" are not considered to be missing data and such be displayed as such.

All missing and partial dates for adverse events or for medications received after enrollment will be queried for a value. If no value can be obtained, substitutions will be made as detailed in Appendix 2. These substitutions will be used in calculations; however, the actual value recorded on the eCRF will be used in all listings.

Missing start and stop times for prior and concomitant antibiotics will be queried for a value. If no value can be obtained but the site indicates the antibiotic was received (onset time) prior to the first dose of test article, 00:01 will be used for the onset time. If the site also indicates that the end time was prior to the first dose of test article, 00:01 will be used for end time. The actual value (blank) will be recorded on the eCRF and will be used in the listings.

Subjects with the designation of treatment relationship of adverse event (AE) and serious adverse events (SAEs) missing will have the worst case assumed to impure the relationship: if relationship to study treatment is missing it will be assumed to be "Yes". The severity and causality assessment for adverse events cannot be missing. Missing data will be queried for a value.

Missing times for assessments of CABP symptoms will be queried for a value. If minutes are not available, the time will be recorded to the closest hour.

If no value can be obtained for all other times for events and assessments occurring after enrollment, the time will not be imputed but will remain missing.

For clinical response, missing data will be handled as follows: For investigator's assessment of Clinical Response at the EOT and PTE Visits:

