11 OTHER RELEVANT DATA ANALYSES/SUMMARIES

11.1 Prior and Concomitant Medications

All medications taken within 7 days prior to the date of informed consent through the Final Follow-up Visit will be recorded on the eCRF. Prior medications will be summarized by WHODRUG (Version 01 Dec 2014) Anatomical Therapeutic Chemical Classification (ATC) level 3 (third level indicates the therapeutic/pharmacologic subgroup) and generic medication name. Medications are considered prior if taken prior to the first dose of test article or if their start date is unknown. Subjects will be counted only once for an ATC class and generic medication name. Concomitant medications taken during and after the study treatment period will be similarly summarized. Medications are considered concomitant if taken on or after the first dose of test article, or if their stop date is unknown or marked as continuing.

The number and percentage of subjects who receive the following prior and concomitant medications will be summarized:

• Systemic antibacterial medications taken within 72 hours prior to first dose of test article and the reasons for receipt (ITT)

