- ^e To be conducted 30 to 37 days after the start of the first dose of test article. The Final Follow-up assessment may be conducted via telephone contact or by another interactive technology for subjects who were considered to be Clinical Successes and had no AEs or clinically significant laboratory, or ECG abnormalities noted at or after the PTE visit. Otherwise, the visit must be conducted in person.
- ^f Written and signed ICF must be obtained before any assessment is performed.
- ^g The investigator should assess the severity of the subject's CABP symptoms of cough, sputum production, pleuritic chest pain, and dyspnea based upon the Community Acquired Bacterial Pneumonia Subject Symptom Severity Guidance Framework for Investigator Assessment (Appendix 3).
- ^h Subjects must have a confirming CXR or CT scan consistent with acute bacterial pneumonia within the 48 hours prior to the first dose of test article.
- ⁱ Only subjects with a PORT Risk Class of II or III for whom oral only treatment for CABP is appropriate are eligible for enrollment.
- ^j Hematology and serum chemistry evaluations will be performed at each of the timepoints indicated. A serum or urine pregnancy test (for women only) and urine dipstick will be performed only at Screening. The relevant local laboratory results from Screening will be used to assess eligibility as per the inclusion/exclusion criteria.
- ^k Treatments that have been administered within the 7 days prior to the date of signing the ICF or during the Screening phase will be recorded in the eCRF. All medications and significant non-drug therapies administered after the first dose of test article must be recorded in the eCRF. Additional information, including start and stop time, will be collected for any prior or concomitant antibiotic.
- ¹ All oral doses should be taken in a fasted state (no food, antacids, or multivitamins containing multivalent cations [eg, aluminum, magnesium, calcium, bismuth, iron, or zinc] or drink except water for at least 6 hours before dosing). Subjects discharged with po test article will be asked to return all unused test article and packaging at each visit and site staff will perform accountability. The total duration of test article therapy for all subjects will be 7 to 10, up to 14 for bacteremia.
- ^m A full physical examination will be completed at Screening, thereafter only changes from Screening measurements should be recorded as AEs in the eCRFs.

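### SAP 10.1 sets a missing stop time of a pre-dose antibiotic to 00:01, which can place the stop before a known start and drops stops on the third day before dosing from the 72-hour count (minor)

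*SAP*

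**What the plan says.** SAP 10.1 deals with antibiotic clock times in three steps.

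- The site is asked first: "Missing start and stop times for prior and concomitant antibiotics will be queried for a value".
- If the query fails and the site indicates that the antibiotic was received "prior to the first dose of test article, 00:01 will be used for the onset time".
- If the site also indicates that it ended "prior to the first dose of test article, 00:01 will be used for end time".

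The blank stays in the eCRF and the listings, so the imputed value matters only in calculations. The rule does not name the date to which 00:01 belongs; the recorded stop date is the natural reading. Nor does it say what to do if the imputed stop precedes a recorded start.

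The output that depends on these times is in SAP 11.1: the number and percentage of ITT subjects with "Systemic antibacterial medications taken within 72 hours prior to first dose of test article". The footnotes to the schedule of events show that the times are wanted: "Additional information, including start and stop time, will be collected for any prior or concomitant antibiotic".

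**The concern.** For an onset, the first minute of the day is the cautious choice, because it makes the exposure start as early as the date allows. For a stop, the same minute is the opposite extreme: it ends the exposure as early as the date allows.

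Two things follow. First, a same-day record with a known start can become impossible. Such records are plausible, because Exclusion 1 in Protocol 6.2 tolerates up to 24 hours of prior therapy and gives a single dose of a daily agent as the example. SAP Appendix 2 has an ordering safeguard for imputed adverse event dates; antibiotic times have none.

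Second, the imputed stop is moved away from the first dose, so an antibacterial really taken inside the 72-hour window can be left out of the SAP 11.1 table. At stake is an accurate description of prior antibacterial exposure in a small study.

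**Working it through.** The documents give no figure to reproduce, so this is date and time arithmetic.

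**Inputs**
- Imputed stop: 00:01 (SAP 10.1), taken to be on the recorded stop date.
- Window: 72 h before the first dose (SAP 11.1).
- First dose: Protocol 7.5.1 says "Subjects should receive their first dose of test article on the morning following enrollment" and gives no clock time. I assume 08:00, with a range of 06:00 to 12:00.
- True stop time: assumed equally likely at any time of the stop date.
- D0 is the date of the first dose; D-1, D-2 and so on are the calendar days before it.

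**Order of start and stop.** With a recorded start of 14:00 and a missing stop time on the same date, 00:01 − 14:00 = −13 h 59 min, so the stop lies 13.98 h before the start.

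**Position relative to the window.** For a stop on D-k and a dose at clock time t, the imputed distance is 24k + t − 1/60 hours. For t = 8:

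| Stop date | Imputed distance before dose | Inside 72 h? |
|---|---|---|
| D0 | 0 + 8 − 0.02 = 7.98 h | yes |
| D-1 | 24 + 8 − 0.02 = 31.98 h | yes |
| D-2 | 48 + 8 − 0.02 = 55.98 h | yes |
| D-3 | 72 + 8 − 0.02 = 79.98 h | no |
| D-4 | 96 + 8 − 0.02 = 103.98 h | no |

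D-2 stays inside even for a dose at 23:59 (48 h + 23 h 59 min − 1 min = 71 h 58 min). D-3 is outside for any dose after 00:01. D-4 lies outside at whatever time the antibiotic was really stopped. So D-3 is the only date on which the imputed time can change the answer.

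**How often D-3 is misplaced.** The part of D-3 inside 72 h is (24 − t)/24:
- 06:00 dose: 18/24 = 75%
- 08:00 dose: 16/24 = 67%
- 12:00 dose: 12/24 = 50%

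**Direction.** The imputed stop cannot be later than a true stop at or after 00:01 on that date, so the error can only remove a subject from the count. If 30 subjects are enrolled, one subject is 1/30 = 3.3 percentage points.

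**With the stop imputed late instead** (earlier of 23:59 and one minute before dose, 08:00 dose): D-3 becomes 72 + 8 − 23.98 = 56.02 h, inside; D-4 becomes 96 + 8 − 23.98 = 80.02 h, still outside; D0 to D-2 do not change side.

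**The case against.** The strongest reply is that very little depends on this rule. It applies only after a failed query, it touches one descriptive table, and three of the four calendar dates that meet the window are classified correctly. All of that stands and sets the severity.

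The word also in SAP 10.1 allows a narrower reading, in which the stop rule applies only when the onset time is missing too. Both times are then 00:01, and with correctly ordered dates no reversal can occur. That reading removes the first effect but not the D-3 effect, and it leaves a known start with a missing stop without any rule.

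The value 00:01 does keep a stop on the dosing date before a morning dose, as the site reported. A cap at one minute before the dose does the same.

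A reader might infer more than the documents support:

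- **That eligibility is affected.** Exclusion 1 does refer to "systemic antibacterial treatment within the 72 hours prior to the first dose of test article", but it is judged at screening, and the SAP lists the deviations recorded in the eCRF. Nothing re-derives it from imputed times.
- **That clinical response is confounded.** Response is the investigator's assessment in the ITT population; no planned analysis adjusts, stratifies or excludes by prior antibacterials.
- **That one-day courses get zero duration.** SAP 10.2.3 computes durations from dates, which gives 1 day.
- **That exposure is always shortened.** If both times are missing, a true course from D-2 20:00 to D-1 06:00 (10 h) becomes 24 h.
- **That Appendix 2 is contradicted.** It covers stop dates that cannot be placed relative to the first dose. SAP 10.1 applies when the site says that the end was before it.

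**Conclusion.** The rule is wrong as written, but its reach is narrow and the severity is minor. It can produce a stop before a recorded start (13.98 h in the example), and it places every D-3 stop with a missing time outside the 72-hour window, although 50% to 75% of that day is inside for a dose between 12:00 and 06:00. The SAP 11.1 count can therefore be too low and never too high. No result for AUC(0-48), safety or clinical response changes.

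This rests on four assumptions: that 00:01 refers to the recorded stop date; that the table is built from date-times and tests the stop against the window; a morning dose at the clock times shown; and, for the percentages, a true stop spread evenly over the day. If the program also tested the start, a D-3 record with a known start inside the window would still be counted. The documents give no basis for estimating how many records will have missing times.

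**What to change.** In SAP 10.1, keep 00:01 for a missing onset time. Replace the stop rule with: a missing stop time is set to the earlier of 23:59 on the recorded stop date and one minute before the first dose, and never earlier than the recorded or imputed start. Say that this applies whether or not the onset time is known.

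The cost is one sentence and a small programming change. The downside is an error in the other direction: every D-3 stop with a missing time is now counted, although with an 08:00 dose 8/24 = 33% of that day lies outside 72 h (25% for 06:00, 50% for 12:00). The 72-hour count may then be slightly overstated. For a table meant to show prior antibacterial exposure, that is the more cautious error.

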10.2 Derived and Transformed Data

10.2.1 Reference Dates

There are three reference dates:

- Because age is an eligibility requirement, the reference date for age is the date of inform consent.
- The safety reference date is the treatment start date and will be used to calculate the study day for safety assessments.
- The efficacy reference date is the date of enrollment and will be used to calculate study day for efficacy measures and baseline characteristics (time since initial diagnosis)

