8.12.2 Clinical Stability

The formal determination of the subject's Clinical Stability will be done programmatically using the investigator's assessment of the subject's vital signs entered into the eCRF. The investigator is not responsible for categorizing the subject's Clinical Stability. Clinical Stability will be determined daily and analyzed by day, EOT, and PTE.

Patients will be considered clinically stable if they achieve all of the following criteria:

- temperature $\leq 37.8^{\circ}C (100^{\circ}F);$
- heart rate ≤ 100 beats/minute;
- RR \leq 24 breaths/minute;
- systolic blood pressure \geq 90 mmHg; and
- arterial oxygen saturation $\ge 90\%$ or PaO2 ≥ 60 mmHg on room air.

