Appendix 1Schedule of Events

Study Phase	Screening ^a		Treatme	nt Phase		Follow	v-up Phase
Study Day ^b		Day 1	Day 2	Day 3	Day 7-10/ EOT ^c	PTE ^d	Final Follow-up ^e
Signed Informed Consent ^f	Х						·
Medical History, current medical conditions, demography	Х						
Assessment of CABP symptom severity ^g	Х		Х	X	Х	Х	
Chest X-ray or CT scan ^h	Х						
PORT Risk Class, ABG (or pulse oximetry) ⁱ	Х						
Blood samples for local lab hematology/chemistry//pregnancy test ^j	Х				Х	X	
Urine samples for local lab urine tests/pregnancy test ^j	Х						
Review of Inclusion and Exclusion criteria/Treatment Group Assignment (if Eligible)	Х						
Test Article Administration and Accountability ¹		X	X	X	Х		
Physical examination ^m	Х		X	X	Х	X	
Vital signs ⁿ							
Height and weight	Х						
Body temperature	X	X	X	Х	Х	X	
Blood Pressure	X	Xº	X	X	X	X	
Pulse Oximetry	X	X	X	X	X	X	
Pulse/Heart Rate	Х	Xº	X	Х	Х	Х	
Respiratory Rate	Х	X	X	Х	Х	Х	

Study Phase	Screening ^a		Treatme	nt Phase		Follow	-up Phase
Plasma samples (in heparin) for PK analyses		X ^p	Xq	Xr	X ^s		
Assessment for need for continued therapy ^t		Х			X		
Investigator's Assessment of Clinical Response					Х	X	
Adverse Events ^u	Х					Х	
Prior/Concomitant Medications and Procedures ^k	Х					Х	
Assessment of Resource Utilization	Х					Х	

ABG = arterial blood gas, AE = adverse event, BP = blood pressure, β -hCG = beta – human Chorionic Gonadotropin, CABP = community-acquired bacterial pneumonia, CT = computed tomography, CXR = chest X-ray, eCRF = electronic case report form, EOT = end of treatment, ICF = informed consent form, IxRS = Interactive Voice Response System/Interactive Web Response System, PK = pharmacokinetics, PORT = Pneumonia Outcomes Research Team, PTE = post-therapy evaluation, RR = respiratory rate, SAE = serious adverse event.

- ^a Following the signing of an ICF, all Screening evaluations, with the exception of the radiographic confirmation of pneumonia, should be completed within the 24 hours prior to treatment group assignment. The radiographic confirmation of pneumonia should be completed within the 48 hours prior to the first dose of test article.
- ^b Study Day 1 is the first day of test article administration. Subsequent study visit days may be consecutive calendar days.
- ^c To be conducted on the day of, or within 2 days following the last dose of test article. Should also be conducted for any prematurely withdrawn subject.

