9.2 Clinical Stability

The formal determination of the subject's Clinical Stability will be done programmatically using the investigator's assessment of the subject's vital signs entered into the eCRF. The investigator is not responsible for categorizing the subject's Clinical Stability. Clinical Stability will be determined daily and analyzed by day, early clinical response window, EOT, and PTE.

Patients will be considered clinically stable if they achieve all the following criteria:

- temperature $\leq 37.8^{\circ}$ C (100°F);
- heart rate ≤ 100 beats/minute;
- RR \leq 24 breaths/minute;
- systolic blood pressure \geq 90 mmHg; and
- arterial oxygen saturation $\ge 90\%$ or PaO2 ≥ 60 mmHg on room air.

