10.2.2 Study day for Safety Measures and Efficacy

If the date of interest occurs on or after the safety or efficacy reference date, then the study day will be calculated as:

Study day = (date of interest – reference date) + 1

There is no safety or efficacy study day 0

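### Efficacy study days are counted from enrollment but the Schedule counts from first dose, so by-day Clinical Stability is labelled one day late for subjects dosed the day after enrollment

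*SAP*

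**What the plan says.** SAP 10.2.1 sets two different anchors for study day. For safety: "The safety reference date is the treatment start date and will be used to calculate the study day for safety assessments". For efficacy: "The efficacy reference date is the date of enrollment and will be used to calculate study day for efficacy measures"; the same sentence also covers baseline characteristics, with time since initial diagnosis as its example. SAP 10.2.2 applies one formula to both, the date difference plus 1, and adds: "There is no safety or efficacy study day 0".

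Protocol 7.5.1 fixes the planned gap between enrollment and dosing: "Subjects should receive their first dose of test article on the morning following enrollment". Footnote b of the Schedule of Events reads "Study Day 1 is the first day of test article administration", and SAP Appendix 1 repeats that definition.

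The output concerned is Clinical Stability. Protocol 8.12.2 says: "Clinical Stability will be determined daily and analyzed by day, EOT, and PTE". SAP 9.2, within the exploratory efficacy measures, says: "Clinical Stability will be determined daily and analyzed by day, early clinical response window, EOT, and PTE". The classification is programmed, "using the investigator's assessment of the subject's vital signs entered into the eCRF".

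**The concern.** The SAP's efficacy day count does not match the study-day definition in its own Appendix 1 or in the protocol. In the planned case the enrollment date is efficacy Day 1 and the first dosing day is efficacy Day 2.

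Two things follow for the by-day display. First, vital signs feed both the safety tables and Clinical Stability, so one reading taken at one visit would carry two different day numbers in the same report. Second, someone reading the stability table would naturally take Day 1 as the first day of treatment. For a subject dosed the next morning, anything falling on efficacy Day 1 was recorded before treatment, and inclusion criterion 4 requires at least two abnormal vital signs at entry. Response over the first days would then appear one day slower than it was.

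SAP section 12, which lists changes from the protocol, does not mention a different Day 1 for efficacy.

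**Working it through.** **Inputs**

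- Efficacy reference: enrollment date (SAP 10.2.1).
- Safety reference: treatment start date (SAP 10.2.1).
- Formula: study day = (date − reference date) + 1 (SAP 10.2.2).
- Planned lag from enrollment to first dose: one calendar day (Protocol 7.5.1).
- Documents' own label for the first dosing day: Day 1 (Schedule of Events, footnote b, in both documents).

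**The documents' own figure.** With the first dose as reference, the first dosing day is (0) + 1 = Day 1. The safety rule reproduces the Schedule.

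**The efficacy rule.** Let enrollment fall on date d and the first dose on d + L. Treatment day k falls on d + L + (k − 1), so its efficacy day is (L + k − 1) + 1 = k + L. The label is shifted by exactly L days.

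| Treatment day k (= safety day) | Efficacy day, L = 0 | Efficacy day, L = 1 (planned) |
|---|---|---|
| 1 | 1 | 2 |
| 2 | 2 | 3 |
| 3 | 3 | 4 |
| 7 | 7 | 8 |
| 10 | 10 | 11 |

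At L = 1 the enrollment date itself is (d − d) + 1 = efficacy Day 1.

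**Mixed lags.** If some subjects are dosed on the enrollment date and others the next day, the efficacy columns combine these readings:

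| Efficacy day | Subjects with L = 0 | Subjects with L = 1 |
|---|---|---|
| 1 | Treatment Day 1 | Pre-dose only |
| 2 | Treatment Day 2 | Treatment Day 1 |
| 3 | Treatment Day 3 | Treatment Day 2 |
| 4 | None scheduled | Treatment Day 3 |

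The last row follows from the Schedule, which plans on-treatment vital signs on Days 1, 2 and 3 and then at EOT (Day 7-10). All three early time points are therefore relabelled or mixed.

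**With the first dose as reference.** The efficacy day is (k − 1) + 1 = k for every L, which agrees with the Schedule and the safety tables.

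**What does not move.** EOT is timed from the last dose and PTE from the last day of therapy (SAP 10.3). PK parameters use actual dosing and sampling times (SAP 10.3), so AUC(0-48) does not depend on study-day labels. SAP 9.2 also names an early clinical response window, but the documents give no days for it, so any effect there cannot be sized.

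**The case against.** The strongest reply is that tables would be built on the named visits. Vital signs are collected at Day 1, Day 2, Day 3 and EOT, SAP Appendix 1 defines Day 1 as the first dosing day, and the SAP 10.3 visit table runs on-treatment from Day 1 to Day 10. On that reading no shift appears. It is a reasonable way to program the table, but the SAP does not state it for efficacy: the visit-window rule in 10.3 is limited to safety outcomes, whereas 10.2.1 prescribes the enrollment date for efficacy study day. The reply shows that the harm is avoidable, not that the text is consistent.

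A second reply is that enrollment suits an ITT analysis, because every ITT subject has an enrollment date and some may never be dosed. That supports enrollment as a fallback, the role SAP 10.3 already gives it for baseline. It does not require it as the anchor for treated subjects in a single-arm study.

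Third, reach is narrow. SAP 9.3 tabulates vital-sign stabilization at EOT only. The by-day analysis rests on SAP 9.2, Protocol 8.12.2 and the synopsis. It is exploratory, and Protocol 12.8 plans no formal comparisons. All of this stands.

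Two stronger readings are tempting and not supported. A reader might infer that every by-day stability result is wrong. Protocol 7.5.1 says only that the first dose should be the next morning, and SAP 10.3 allows baseline on Day -1 or Day 1; a subject dosed on the enrollment date has no shift. A reader might also express one day as a share of a 7- to 10-day course, 1/10 = 10% to 1/7 = 14%. That is an offset in a label: no treatment day, observation or subject is lost, and each reading's stable or not-stable classification is unchanged.

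**Conclusion.** The inconsistency is real and small. Taken as written, SAP 10.2.1 and 10.2.2 label by-day Clinical Stability one day later than the Schedule of Events and the safety tables for each subject dosed the calendar day after enrollment, which is the planned case. If the lag is one day for everyone, the percentages are unchanged and only the column headings are wrong. If lags of 0 and 1 both occur, readings from different treatment days are pooled under one label, and the percentages themselves can change.

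This rests on two assumptions: that the by-day table uses the derived study day, as 10.2.1 directs, and that enrollment and first dose fall on different calendar dates. The documents do not say how many subjects will have each lag, so the amount of pooling cannot be estimated. The consequence stays within an exploratory, descriptive display; Clinical Response at EOT and PTE, the primary AUC(0-48) comparison and the sample size are untouched.

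**What to change.** Amend SAP 10.2.1 to say that study day for by-day efficacy measures, meaning Clinical Stability, is counted from the date of first dose so that it matches the Schedule of Events, with the enrollment date used only for ITT subjects who are never dosed, as SAP 10.3 already does for baseline. Keep enrollment as the reference for baseline characteristics such as time since initial diagnosis. Moving the whole efficacy reference date to first dose would shift that variable's anchor as well, which is not needed.

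The cost is a sentence or two in the SAP before database freeze. The dates of enrollment and first dose are already needed for the existing rules, so no new data are required and no other analysis changes.
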